3.1.2 Secondary outcomes of the feasibility study

- (i) The overall level of attrition (failure to attend the final 2-year visit), and a comparison of attrition between open label and blinded practices.
- (ii) Costs of blinded versus open label study designs.
- (iii) Comparison of incidence of serious adverse events between vitamin D and control in blinded practices.
- (iv) Comparison between vitamin D and control of numbers of infections, GP prescriptions and GP visits (a) in blinded practices, and (b) in open-label practices. This will provide an estimate of the bias in these measures in participants allocated to vitamin D in an open control design.
- (v) Blood 25(OH)D concentration at recruitment and at 2 years in relation to allocated treatment and other potential determinants of vitamin D status (self-reported sun exposure, diet and use of vitamin D supplements).
- (vi) Comparison of change in systolic and diastolic blood pressure from recruitment to 2 years between vitamin D and control groups.
- (vii) Cause-specific mortality and cancer incidence will be ascertained by flagging in the National Health Service Information Centre (NHS IC).
- (viii) Hospital records will be collected by NHS number linkage with the Hospital Episode Statistics (HES) database.

3.1.2 Additional trial assessments

Before randomisation:

- 1) The practice nurse will record details of foreign holidays, sunbathing, sunbed use and use of vitamin supplements on the online Case Report Form (CRF) at the GP practice with all participants before randomisation.
- 2) A blood sample will also be taken, and corrected serum calcium will be assayed before randomisation to establish eligibility. Aliquots (plasma and buffy coat) will be stored in liquid nitrogen for 25(OH)D assay at the end of the study, and (subject to additional funding and optional additional consent) for further analyses including genetic studies.

At two years:

- 1) All 1600 participants will attend the GP practice 2 years after randomization. A further blood sample for 25(OH)D assay and responses to the same questions asked at recruitment will be obtained to quantify differences in vitamin D status and factors that may affect it between the intervention and control groups in blinded versus open label studies.
- 2) Summaries of GP records for all participants will also be extracted for GP visits, prescriptions and infections for one year pre-randomisation and 2 years post-randomisation.

3.2 ADDITIONAL UNFUNDED STUDIES

The participant information sheet will explain that there are many possible effects of vitamin D and that we hope to obtain further funding and ethical approval for more extensive analyses of blood samples (including genetic studies). Optional additional informed consent will therefore include permission (subject to further ethical approval) for long-term storage and unspecified analyses, including genetic studies, of the blood samples taken at entry and 2 years.

3.3 RISKS AND BENEFITS

There are many suggested benefits of vitamin D supplementation for human health (Holick, 2007). Those reported in meta-analyses include prevention of fractures (Bischoff-Ferrari et al., 2005) and falls (Bischoff-Ferrari et al., 2004) and reduction in all-cause mortality (Autier and Gandini, 2007).

Vitamin D supplementation is generally very safe; the principal risk relates to the very rare phenomenon of vitamin D hypersensitivity (Vieth, 1999). This manifests as hypercalcaemia, and may arise in individuals with hyperparathyroidism or granulomatous disease (Sharma, 2000). We seek to minimize the risk of harm arising from administration of vitamin D to study participants by the following measures:

- 1. Baseline exclusion of participants at increased risk of vitamin D hypersensitivity (i.e. those with baseline hypercalcaemia); those known to have active tuberculosis, sarcoidosis, hyperparathyroidism, past or present nephrolithiasis, vitamin D intolerance, referral for suspected hepatic or renal dysfunction, any malignancy other than non-melanoma skin cancer not in remission for ≥ 3 years; and those taking oral 1-alpha-hydroxylated vitamin D preparations (e.g. alfalcalcidol, calcitriol) or the combination of a thiazide diuretic (e.g. bendrofluazide, metolazone) with a calcium supplement; or a dietary supplement containing or equivalent to more than 400 IU (10 micrograms) per day vitamin D.
- 2. Ensuring that all participants are aware of symptoms of hypercalcaemia, and advising them to contact their GP if they develop these symptoms, so that their GP can arrange for a blood test for hypercalcaemia (and report hypercalcaemia as a suspected adverse reaction to the Trial Coordinating Centre).

- 3. Three-monthly monitoring of participants for study medication compliance (and reasons for non-compliance) and hospital admissions (excluding outpatient visits and A&E attendances which do not result in admission).
- 4. Instituting therapy for hypercalcaemia for any study participant developing this complication: usually hypercalcaemia is effectively managed by simple rehydration, but effective pharmacological interventions are also available if hypercalcaemia does not resolve with rehydration alone (Bushinsky and Monk, 1998).

4. PARTICIPANT ENTRY

4.1 PRE-RANDOMISATION OR PRE-REGISTRATION EVALUATIONS

Participants will undergo a blood test at the screening visit to detect possible hypercalcaemia before randomisation. Individuals with a baseline corrected serum calcium level > 2.65 mmol/L will be excluded from the trial (see section 5.1.3).

4.2 INCLUSION CRITERIA

- Age \geq 65 years and \leq 84 years at enrolment
- Contactable by telephone, able to receive recorded deliveries by post, and able to attend enrolment at the GP surgery
- GP notes for the previous year are available

4.3 EXCLUSION CRITERIA

- Known active tuberculosis, sarcoidosis, hyperparathyroidism, past or present nephrolithiasis, vitamin D intolerance, referral for suspected hepatic or renal dysfunction, terminal illness, any malignancy other than non-melanoma skin cancer not in remission for ≥ 3 years
- Planning to move from the GP practice or to emigrate within 5 years
- Any other condition that in the PI's or CI's judgement might compromise participant safety or compliance, interfere with evaluation or preclude completion of the study.
- Baseline corrected serum calcium > 2.65 mmol/L
- Taking dietary supplement or other medication containing more than 400 IU (10 micrograms) per day vitamin D
- Concomitant therapy with any of the following: carbamazepine, phenobarbital, phenytoin, primidone, digoxin, oral 1-alpha-hydroxylated vitamin D preparations (e.g. alfalcalcidol, calcitriol) or the combination of a thiazide diuretic (e.g. bendrofluazide, metolazone) with a calcium supplement
- Treatment with any other investigational medical product or device up to 4 months before first dose of IMP

4.4 WITHDRAWAL CRITERIA

Treatment may be interrupted or discontinued permanently by participant choice or at the GP's discretion. This will be monitored, but participants will remain under follow-up. The main analyses will be by intention to treat, so the only participants withdrawn from the trial will be those who specifically withdraw consent for further passive follow-up through national record systems (NHS Information Centre) and GP records. No further follow-up will be arranged for withdrawn participants after this point. Data collected up to the time of

withdrawal will be included in study analyses unless participants specifically withdraw permission to do so.

5. ENROLMENT AND RANDOMISATION PROCEDURE

5.1 RANDOMISATION OR REGISTRATION PRACTICALITIES

5.1.1 Trial application and database

Online CRF (VIDAL App): This web based application will be held on a secure server at The Cancer Prevention Trials Unit at Queen Mary University of London (see section 12). Each practice will only have access to its own participants' full records, whereas the Trial Coordinating Centre will have access to data collected after consent for the purposes of contacting participants, sending study medication, monitoring sites, flagging etc. For monitoring purposes the Trial Coordinating Centre will also have access to the anonymous record of the initial telephone call by the practice nurse (see below). This anonymous record will contain only the local study identifier and yes/no responses to eligibility items.

Allocation of practices to open label or double-blind randomisation

Before the study begins, practices will be randomised within matched pairs (see 5.1.5) to the blinded study or open control study.

Pre-consent Spreadsheet: Study recruitment will take place through 20 GP practices. In the first instance, each GP practice will generate a locally stored spreadsheet listing all registered patients aged 65-84 (including NHS number, name, sex, date of birth, address and telephone number) for the purpose of screening and inviting potentially eligible patients to participate in the trial.

The practice nurse will screen the GP notes of each participant in the spreadsheet to exclude ineligible participants, including those judged to lack the mental capacity to give informed consent. Eligibility of respondents will be confirmed by the local PI (GP) before sending out study invitations by post. Respondents will then be telephoned by the practice nurse to confirm eligibility. Before this call, the practice nurse will access the online VIDAL app to create a new anonymous record for the respondent, entering only the components of a unique local identifier for each participant (from the spreadsheet), then entering eligibility items during the call. The unique local identifier will be automatically derived by the VIDAL app once the practice nurse has entered the participant's first and last initial, and the two-digit day of their date of birth. These items will be added to a 2-letter practice code and a 4-digit line number to create a local unique identifier for each participant. Potentially eligible participants will then be offered a screening visit appointment where informed consent will be obtained from those agreeing to participate in the trial. The unique participant identifier and dates of pre-consent correspondence and telephone calls will be recorded on the spreadsheet, which will be held on the practice computer and not otherwise accessible.

After reviewing participant eligibility and obtaining informed consent at the screening visit, the practice nurse will access the VIDAL app to enter the participant's personal details (including NHS number, name, sex, date of birth, address and telephone number), record baseline systolic and diastolic blood pressure, height, weight and waist circumference, administer the online CRF questions and take the baseline blood samples. The practice nurse may delegate some responsibilities to appropriately trained, named practice staff (eg height, weight and waist circumference measurement, administration of lifestyle questions or taking blood). The practice may also initially administer a paper copy of the

baseline visit questions if required in consultation with the Trial Coordination Centre. Apart from paper copies of the baseline visit data, signed informed consent and any postal responses from participants, including postal replies to 3-monthly follow-ups, the VIDAL app will constitute the source data (an electronic CRF). Upon completion of the screening visit, a copy of the signed informed consent form will be sent to the Trial Coordination Centre.

After verifying participant eligibility (by checking the copy of the informed consent form and the online blood calcium result) the Trial Coordinating Centre will telephone the participant to confirm that they are still willing to be randomised. The current date, a unique trial number and the allocated medication pack number will then be added to the VIDAL app automatically, and the pharmacy will be instructed to send that medication pack to the participant. The VIDAL app will contain details of all subsequent participant contacts, including: sending and receipt of first (at randomisation) and second (at 1 year) treatment packs, monthly automated telephone, e-mail or text message reminders to take medication, 3-monthly follow ups (dates due, sent and acknowledgement received), 2-year blood sample, adverse event reports, address changes, and any other notes by practice staff. Apart from postal and e-mail communications from participants and from the GP practice to the Trial Coordinating Centre, the VIDAL app will thus constitute the primary data source on follow-up after randomisation. All items will be accessible by the Trial Coordinating Centre and the relevant practice.

If at the initial visit a participant is found to be ineligible or does not consent to participate in the trial, the date of the visit and reason for non-participation (but no identifying or other data) will be added to their anonymous record on the VIDAL app.

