- (ii) Participants in unblinded practices will be randomised to receive either 100,000 IU monthly (average 3300 IU/day) of oral vitamin D3 (5 ml Vigantol® Oil) monthly for 2 years or open control (no treatment): 800 participants

[figure not shown]
DURATION Recruitment 1 year, treatment duration 2 years, study duration 3 years

VIDAL Trial Protocol Page 14 of 45 Version 3, 25.07.2012

STUDY FLOWCHART

Cluster randomisation within 10 matched pairs of GP practices between open randomisation with untreated controls, or double-blind randomisation with placebo control

Exclusions based on review of GP records:

[figure not shown]
Aged <65 or >84 years, no telephone, terminal illness, known active tuberculosis, referral for suspected hepatic or renal dysfunction, known sarcoidosis, hyperparathyroidism or nephrolithiasis, <3 years since remission from cancer (except non-melanoma skin cancer), taking >400 IU daily vitamin D, any other Investigational Medicinal Product (IMP) therapy within 4 months, concomitant carbamazepine, phenobarbital, phenytoin, primidone, digoxin, oral 1-alphahydroxylated vitamin D preparations (e.g. alfalcalcidol, calcitriol) or the combination of a thiazide diuretic (e.g. bendrofluazide, metolazone) with a calcium supplement

18,000 potentially eligible participants aged 65-84

Send description of appropriate trial and invitation to visit practice for informed consent, blood sample, blood pressure and lifestyle questions

Target enrolment: 1600 (9% of eligible participants)

Visit attended, signed informed consent taken, blood pressure measured, lifestyle questions completed, blood sample taken and aliquot stored, corrected serum calcium ≤ 2.65 mmol/L

At 24 months post-randomisation on all 1600 participants:

- (i) Repeat lifestyle questions, blood pressure measurement and blood sample to measure serum 25-hydroxyvitamin D concentration.
- (ii) Flagging for lifelong follow-up through national registers for death and cancer registration, and tracing through HES for hospital admissions and diagnoses.
- (iii) GP note abstraction: GP visits, prescriptions and infections over preceding 3 years.

VIDAL Trial Protocol Page 15 of 45 Version 3, 25.07.2012

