3.1 STUDY OUTCOME MEASURES

3.1.1 Primary outcomes of the feasibility study

The primary aim of the feasibility study is to establish the procedures required to conduct the main trial: our target is to randomise 1,600 participants aged 65-84 through 20 GP practices.

Primary outcome measures:

- 1. The overall recruitment rate (the proportion of invited participants who are randomised) and comparison of recruitment rate in blinded versus open control studies.
- 2. The overall level of compliance with study medication and comparison of blinded medication versus open label vitamin D compliance (to evaluate whether participants taking open label vitamin D are more or less compliant than those who are unaware of IMP status). A randomized participant is defined as compliant:
- (i) If allocated to vitamin D: they report taking at least 19 (79%) of the 24 monthly doses of allocated IMP, and attend the 2-year follow-up visit.
- (ii) If allocated to no vitamin D (whether placebo or open control): they report taking a total of <300,000 IU of vitamin D supplements over the 2 years of the study, and attend the 2-year follow-up visit. (The current UK RDA of 400 IU/day is 292,000 IU over 2 years).

These will be combined as a single outcome measure, which is the number of people we must invite to get one person complying with allocated treatment, to demonstrate that the main trial is feasible. It equals the number invited divided by the number randomised and compliant.

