9.3 STATISTICAL ANALYSES

9.3.1 Main clinical analyses

The main analyses will be the matched-pair comparison of recruitment and overall compliance rates between blinded and open control designs. Details of additional vitamin D supplement use will be recorded at entry, and retrospectively at the 2-year final visit. Failure to report taking at least 19 doses of allocated IMP or to attend the 2-year final visit are included in the definition of non-compliance, so there will be no missing data for the main analyses.

Change in blood level of 25(OH)D from entry to exit will be analysed in relation to self-reported compliance. The effect of treatment on 25(OH)D level, both overall by allocated treatment and in compliant participants, will also be analysed in relation to the pre-treatment 25(OH)D level.

The principal economic issues in the feasibility study will be the overall additional trial costs in blinded practices, to be weighed against the advantages and disadvantages of placebo control in relation to possible bias in self-reporting of minor conditions and suspected side-effects, treatment compliance, and self-medication with vitamin D by controls. The feasibility of collecting appropriate resource use data will also be assessed, specifically the viability of linking HES data to NHS reference costs using Healthcare Resource Group (HRG) information in order to calculate NHS costs, and using participants' medical records to obtain information on the use of primary care services.

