9.3.2 Subgroup analyses

25(OH)D level (pre-treatment, and change after 2 years of treatment) will be analysed in sub-groups of 5-year age group and sex. The change in 25(OH)D level will also be analysed in relation to pre-treatment level, adjusted for the negative bias in this correlation. The overall recruitment rate among all registered patients in each practice will also be analysed in sub-groups of age and sex. (A tabulation by 5-year age group and sex of all registered patients will be obtained from each practice for this purpose.)

All analyses will be repeated in subgroups based on pre-treatment blood 25(OH)D level.

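### The open v. blinded recruitment comparison uses an invited count formed after practices are allocated; add the same comparison per registered patient

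*Protocol*

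**What the plan says.** **Order of events.** Section 5.1.1 states: "Before the study begins, practices will be randomised within matched pairs (see 5.1.5) to the blinded study or open control study". The study flowchart in the Study Summary also puts cluster randomisation ahead of exclusions from GP records. After allocation, "The practice nurse will screen the GP notes of each participant in the spreadsheet to exclude ineligible participants". Section 5.1.1 adds: "Eligibility of respondents will be confirmed by the local PI (GP) before sending out study invitations by post". (Section 5.1.2 describes a GP check after the reply slip comes back; the nurse's screening precedes the mailing in either account.) The flowchart instruction "Send description of appropriate trial and invitation to visit practice for informed consent" means that the mailing is specific to the practice's design.

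**Discretion.** Most exclusions in section 4.3 are specific conditions or drugs. One is not: "Any other condition that in the PI's or CI's judgement might compromise participant safety or compliance".

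**Outcomes.** Section 3.1.1 defines the recruitment rate as randomised over invited and defines compliance among randomised participants. It says the compliance comparison is meant to show whether awareness of treatment changes compliance. On the two together it says: "These will be combined as a single outcome measure, which is the number of people we must invite to get one person complying". That measure is the number invited divided by the number randomised and compliant, and its stated purpose is to show that the main trial is feasible.

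**Analyses.** Section 9.3.1: "The main analyses will be the matched-pair comparison of recruitment and overall compliance rates between blinded and open control designs". Section 9.3.2: "The overall recruitment rate among all registered patients in each practice will also be analysed in sub-groups of age and sex", from an age and sex tabulation of all registered patients obtained from each practice for that purpose. Section 9.2 says that all eligible patients in each practice will be invited.

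**The concern.** Cluster randomisation protects a comparison whose denominator is fixed before allocation. The invited list is not fixed then: it is drawn up afterwards by practice staff, and one criterion lets them exclude on expected compliance. Nothing in the protocol conceals the design from staff while they screen. That they know it then is an inference from the stated order, but a reasonable one. The pre-consent spreadsheet stays on the practice computer, and the coordinating centre's anonymous record begins only with the telephone call to respondents, so differential screening before mailing would be hard to see centrally.

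A practice that leaves more unlikely joiners off its list shows a higher recruitment rate with no more people recruited. The open v. blinded contrast is a declared aim of the study and is meant to inform the design of a trial of 20,000. A per-registered-patient rate has a denominator that allocation cannot influence, and the counts are already to be collected, but the protocol assigns them only to age and sex subgroups.

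A related point is interpretation. Compliance is compared among people who joined after reading about their practice's design, so a difference may reflect who joined and not what awareness of treatment did.

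**Working it through.** **1. The plan's own figures.** Section 9.2 gives a standard error of 0.2% for a 9% rate. With the 18,000 potentially eligible people of the flowchart, √(0.09 × 0.91 / 18,000) = 0.0021, which agrees. Per practice, 18,000 / 20 = 900 and 80 / 900 = 8.9%, which also agrees. The 92% power for 10% v. 15% cannot be settled, because the distribution behind the quoted ranges, the within-pair correlation and the test are not stated. Plausible choices gave from 23% to over 99%. Nothing below depends on that figure.

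**2. Effect of list length on the rate.** If the true rate is r and a fraction s of the list is omitted, all of them people who would not have joined, the observed rate is r / (1 − s). For example, 0.10 / 0.90 = 11.1%.

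**3. Chance of a false design effect.** Simulation with:
- 10 matched pairs and 900 potentially eligible people per practice
- true mean rate 10% in both designs
- practice rates normal, with the protocol's 2.5–17.5% range read as ±1.96 SD or ±3 SD
- within-pair correlation 0, 0.5 or 0.7
- paired t test on rates, two-sided 5%
- extra omission s in one design only

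The values of s are assumptions; the protocol gives none.

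| s | 10% reads as | False positives, invited denominator | False positives, fixed pre-screen denominator |
|---|---|---|---|
| 0 | 10.0% | 5% | 5% |
| 5% | 10.5% | 6–9% | 5% |
| 10% | 11.1% | 9–23% | 5% |
| 20% | 12.5% | 20–73% | 5% |
| 33% | 15.0% | 51–99% | 5% |

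**4. What this requires.** The omitted people must be those who would have declined. With 80 joiners and a list cut from 900 to 720, the rate goes from 80/900 = 8.9% to 80/720 = 11.1% only if all 180 omitted would have declined. If omission is unrelated to willingness, the expected joiners are 80 × 720/900 = 64, and 64/720 is again 8.9%. Producing the full 10% v. 15% contrast by screening alone would need a third of one design's list omitted, all of them decliners.

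**5. The combined measure.** At 9% recruitment and 90% compliance (assumed), it is 1 / (0.09 × 0.90) = 12.3 invited per complier. With a list 10% shorter and the same compliers, it is 0.90 / (0.09 × 0.90) = 11.1. It carries the same distortion.

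**6. Compliance among joiners.** Take the protocol's 10% v. 15% participation. Suppose 10 per 100 join under either design and comply at 95%, and the extra 5 comply at 65% (assumed). Observed compliance in the second design is (10 × 0.95 + 5 × 0.65) / 15 = 12.75 / 15 = 85%. That gives 95% v. 85%, the example difference in section 9.2, with awareness affecting nobody. Invited per complier points the other way: 1 / (0.10 × 0.95) = 10.5 v. 1 / (0.15 × 0.85) = 7.8.

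**7. Limit of the registered denominator.** Section 9.1 has some practices continuing past 80 only if others fall short, and the section 9.2 power simulation counts approaches needed to reach 80. Suppose two practices with 900 potentially eligible and true rates of 10% and 15% both stop at 80. They would approach about 80/0.10 = 800 and 80/0.15 = 533, so the invited rate shows 10% v. 15%. On the fixed base both read 80/900 = 8.9%, and a real difference disappears. The per-registered rate is therefore an addition, not a replacement.

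**The case against.** The case against is substantial. Section 9.2 requires all eligible patients to be invited, most exclusions can be read from the notes, and the documents give no reason why either design would screen harder. A 5% difference in screening does little. Section 9.3.2 already plans recruitment per registered patient, and applying it between designs could be left to an analysis plan that is not shown. These points limit the likely size. They do not close the route, because eligibility itself contains a judgement about compliance, and section 9.3.1 names the main comparisons without a registered-patient version.

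A reader might infer more than the documents support:
- *That neither comparison is protected by randomisation.* Practices are randomised to a design, and the third study aim is that design's effect on recruitment and compliance. Who joins is part of the effect, and the main trial would enrol those joiners. Joiner selection is a bias only for the reading about awareness of treatment.
- *That the combined outcome is a safe alternative.* It uses the same invited count (step 5).
- *That 3.1.1 and 9.3.1 conflict.* Section 3.1.1 lists both separate comparisons as primary and gives the combined measure another purpose.
- *That invitation lists must be locked before allocation is disclosed.* That would mean screening every list first, with recruitment then running for a year and eligibility going out of date. It is debatable and not needed here.

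**Conclusion.** The point holds in a limited form. The main open v. blinded recruitment comparison rests on a denominator formed after allocation by staff with some discretion, so differential screening could mimic or hide a design effect. The combined outcome does not cure this. The size is unknown: about 6–9% false positives if screening differs by 5%, and 9–23% if by 10%, assuming every extra omission would have declined and only one design is affected. The 2.2-point shift from 8.9% to 11.1% illustrates an extreme and should not be read as an expected bias. No stated figure in the protocol is shown to be wrong. Compliance among those randomised remains a useful planning quantity, but it does not isolate the effect of knowing one's treatment.

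**What to change.** In section 9.3.1:
- Keep the invited-based comparison.
- Add the same matched-pair open v. blinded comparison with all registered patients aged 65–84 as denominator, once for randomised and once for randomised-and-compliant participants, using the tabulations obtained under 9.3.2.
- Compare the proportion of registered patients invited between designs. This is a direct check on differential screening and needs only counts already required.
- Interpret the per-registered rates only for practices where all eligible patients were invited, which in a paired analysis means pairs where both did so. Record for each practice whether invitation was complete.

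In section 3.1.1, describe compliance among those randomised as a property of each design's joiners, and remove the suggestion that it measures the effect of awareness.

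The cost is a little extra analysis and some wording. The registered denominator includes ineligible people, so its rates will be lower than the invited-based ones. If some practices stop near 80, fewer than 10 pairs will be interpretable on that base.
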